5.3 Randomisation

As part of the implementation of the CYPHP Evelina London model within Lambeth and Southwark, GP practices are grouped into virtual clusters. Clustering is a pragmatic clinical delivery decision, because it allows sharing of resources and holding specialist in-reach clinics without added expense to the practices. Where possible clusters were created aligned to GP Federation "neighbourhoods" or other groupings.

Of the 100 GP practices within Lambeth and Southwark, 25 took part in pilot testing of some components of the CYPHP Evelina London model of care to refine the model and test feasibility. As such these 25 practices are not randomised. All other practices are eligible to take part in the trial evaluation.

Randomisation is at the level of the primary care practice cluster. 23 clusters were randomised, by an external statistician.

Randomisation was stratified by borough, and restricted with the following restriction factors:

- Baseline Index of Multiple Deprivation (IMD) / Income Deprivation affecting children Index (IDACI) score per cluster
- CYP population <16 per GP cluster
- Paediatric OP referrals 2015-2016

These restrictions factors are believed to affect health related quality of life and patterns of health service use. Restricted randomisation on these factors helps to ensure that clusters are comparable with regards to (i) number of patients within each cluster, (ii) the socio-demographic profile of their patient population (iii) the referral patterns within clusters.

5.4 Blinding

The study statistician, health economist, and researchers involved in recruitment will be blind to group allocation. The statistician and health economist will only have details of participants by study number and pseudonymised patient ID.

The evaluation will not be blinded at the level of the service delivery or participant.

6. DATA

Data will be extracted from three main sources:

- 1) Primary care (GP) clinical administrative systems
- 2) Secondary care (hospital) clinical patient administrative systems
- 3) Survey/questionnaire data (consented patient level) from a patient portal
 - a. Note: For service evaluation, Health Check data are also available.

6.1 Primary care clinical data

All practices within Lambeth and Southwark use the Egton Medical Information System (EMIS). Agreements on sharing data have been made between CYPHP and the GP federations for Lambeth, Southwark North and Southwark South. We will receive data on all children aged <16 registered with Lambeth and Southwark GP practices. Extractions will take place every quarter (3 months). See Data and reporting guidelines document for more details.

6.2 Secondary care clinical patient data

All hospital activity is recorded within the patient administrative system (PAS). The activity of interest to our evaluation is:

- Admitted patient care data
- A&E data
- Outpatient data

Agreements on sharing data have been made between CYPHP and the trusts in Lambeth and Southwark - Guy's and St Thomas's (GSTT) and King's College Hospital (KCH). We will receive quarterly extracts of health care activity at St Thomas's, Guy's or King's College Hospitals of

children registered with Lambeth and Southwark GP practices. Local coding (within St Thomas's, Guy's or King's College Hospitals) is completed within a month of a patient's health activity, with a freeze date of 6 weeks after the activity. This will mean the coding will be relatively stable and few changes will be made after 2 months of patients' activity/discharge.

6.3 Survey/questionnaire data from CYPHP Health Check

Patient/parent-reported measures are collected when parents complete a health check for their child. These are listed below and described in section **Error! Reference source not found.**

- Mental health and wellbeing using the Strengths and Difficulties Questionnaire (SDQ) (all patients)
- Asthma severity using the Asthma Control test (ACT) (Asthma patients)
- Constipation severity as measured by CYPHP Constipation Score (Constipation patients)
- Eczema severity using the Patient Oriented Eczema Measure (Eczema patients)
- Demographics
 - Language most commonly spoken at home
 - CYP Age
 - CYP Gender
 - CYP Ethnicity (categories in Appendix)
 - Carer Ethnicity (categories in Appendix)
- Social Questions
 - Do you have concerns about your housing situation?
 - Do you always have enough food for your family?
 - Do you ever struggle to pay your household bills?
 - Do you have any concerns about your mental wellbeing?
 - Do you or anyone else in the household smoke?
 - What is your employment status?

6.4 Survey/questionnaire data from study database

Once the patient has consented to the study the participants will be asked to complete further questionnaires (listed below). These are described in section **Error! Reference source not found.**

- PedsQL
- CHU9D
- WEMWBS
- School & Work Absence Questions
 - How many days of school has your child missed due to ill health or attending health-related appointments in the past three months?
 - How many days of work have you missed in the past three months due to your child's illness or healthcare appointments?

Follow-up data is collected at 6 and 12 months (+ up to 4 months) following baseline data collection. At the follow-up time points the Health Check questionnaires are also repeated.

The schedule of events for the tracer condition analysis of CYPHP is displayed in Table 1.

Table 1: Schedule of data collection for CYPHP Tracer Condition Questionnaires

	Procedures	CYPHP Health Check	Baseline Study Questionnaires	CYPHP Service entry	6-month Follow-up Study Questionnaires	12-month Follow-up Study Questionnaires
Health Checks	ACT	C			C	C
	POEM	C			C	C
	Constipation questionnaire	C			C	C
	SDQ	X			X	X
	Social Questions	X			X	X
	Health Check Demographics	X				
Evaluation Questionnaires	Eligibility assessment		X			
	Informed consent		X			
	PedsQL		X (1° child outcome)		X (1° child outcome)	X (1° child outcome)
	CHU9D		X		X	X
	WEMWBS		X (1° parent outcome)		X (1° parent outcome)	X (1° parent outcome)
	School & Work Absence Questions		X		X	X
CYPHP Services	Offer of CYPHP Services			Requires registration with GP in intervention arm and clinical need identified at Health Check triage		
	Receipt of CYPHP Services			Receive service if: Parent/carer/CYP agrees and takes up service		

X: collected on all participants

C: collected on participants with the relevant condition

6.5 Data linkage

Pseudonymised patient identifier

Each patient identified will be assigned a pseudonymised ID based on their NHS number. The pseudonymised ID will allow linkage of CYP's health records across data sets (primary and secondary care) and longitudinally over time.

Information on the pseudonymisation process can be found in the CYPHP Data Management Plan.

7. STUDY TIME PERIODS

7.1 Study timeline and trial periods

CYPHP Funded: October 2016

Staff Recruitment: 1 October 2016 – 31 March 2017

Trial and Service Set up, intervention embedding: 1 April 2017 – 31 March 2018

Trial start: 1 April 2018

Trial period ends: 30 June 2021

See diagram in Appendix.

Baseline health service use data: Use annual rate(s) for financial year(s) (April-March) for 2014/15, 2015/16, 2016/17 (omitting 2017/18 as during set-up period service implementation began in some areas). Using annual rates avoids issues of seasonality. Where only one year of baseline data is needed, use 1 Apr 2016-31 Mar 2017.

Secondary analysis: Using the trial time period 1 July 2020 - 30 June 2021 (the period with most complete embedding of services).

7.2 Before/After Analyses and Interrupted Time Series

Before/After analyses

- In the control (EUC) arm, we will compare outcomes during the trial period with outcomes prior to the trial.
- In the intervention arm, we will compare outcomes with those observed prior to CYPHP.
 - A) Randomised intervention clusters only
 - B) Pilot and intervention clusters (i.e. quasi-experimental population)

Interrupted Time Series

- Interrupted Time Series analyses will be conducted using the time periods described above.

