18. PROTOCOL DEVIATIONS

18.1 Protocol changes related to COVID-19 Pandemic

Due to the COVID-19 pandemic, there was a trial pause, 12MAR2020 – 04JUL2020. Any individual consented data collection that occurred during the pause was repeated after the pause. Also, for participants enrolled in the study before the pause, the time points for follow-up data collection after the pause were delayed by the length of this pause, to ensure all study participants had the opportunity to be exposed to the intervention (or control) for the relevant time periods (6 months and 12 months) before follow-up data collection. Data collected during the pause may be used for secondary analyses. See appendix for diagram.

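### The before/after and interrupted time series analyses in SAP 7.2 have no between-arm contrast and no pandemic handling, so a COVID shift in service use cannot be separated from a CYPHP effect

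*SAP*

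**What the plan says.** Section 7.2 sets up three supplementary analyses.

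- **Control arm:** "In the control (EUC) arm, we will compare outcomes during the trial period with outcomes prior to the trial".
- **Intervention arm:** "In the intervention arm, we will compare outcomes with those observed prior to CYPHP". This is done in two versions: (A) the randomised intervention clusters only, and (B) those clusters pooled with the pilot clusters, which section 5.3 says were not randomised.
- **Time series:** "Interrupted Time Series analyses will be conducted using the time periods described above".

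The periods come from section 7.1. For the baseline: "Use annual rate(s) for financial year(s) (April-March) for 2014/15, 2015/16, 2016/17", or, if one year is enough, "Where only one year of baseline data is needed, use 1 Apr 2016-31 Mar 2017". The set-up year 2017/18 is left out. For the trial: "Trial start: 1 April 2018" and "Trial period ends: 30 June 2021". Section 7.1 also names a secondary window, 1 July 2020 to 30 June 2021. Section 8.1, however, defines the health service use population on a study period of April 2018 to June 2020.

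On COVID, section 18.1 states that "there was a trial pause, 12MAR2020 – 04JUL2020" and deals with repeating or delaying consented questionnaire collection. Section 12.1 lengthens the observation time for the asthma quality indicators. Neither provision reaches the analyses in 7.2.

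**The concern.** A before/after comparison within one arm attributes to the arm everything that changed between the two periods. Here the before period ends on 31 March 2017, and the after period runs into, and on the 7.1 dates well through, the pandemic. Hospital and primary care use may have moved for reasons unrelated to the model of care, and the plan as written has no device to take that movement out: no between-arm contrast of the changes, no calendar term, no truncation and no comparison series for the time series.

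At stake is the interpretation of pre-specified results that may be reported next to the trial's main finding. If service use fell in the pandemic, the intervention-arm estimate is biased towards benefit. If it rose, as could happen for some contact types, it is biased the other way.

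**Working it through.** The SAP gives no figure for the pandemic share, so there is none to reproduce. The check has four steps.

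**1. Share of the after period exposed.** The start of the trial pause, 12 March 2020 (18.1), is used as a proxy for the start of the pandemic. Days are counted inclusively from 1 April 2018.

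| After period | Total days | Days from 12 Mar 2020 | Share p |
|---|---|---|---|
| Section 7.1: to 30 June 2021 | 1187 | 476 | 476/1187 = 40.1% |
| Section 8.1: to 30 June 2020 | 822 | 111 | 111/822 = 13.5% |
| Window 1 July 2020 to 30 June 2021 | 365 | 365 | 100% |

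Moving the proxy date matters little: on the 7.1 dates the share is 41.0% from 1 March 2020 and 38.4% from 1 April 2020.

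**2. Spurious change with no CYPHP effect.** Let f be the proportional fall in the event rate during the exposed days. If the rate is otherwise constant and person-time is spread evenly over the period, the apparent before/after rate ratio is 1 − p × f. The documents give neither the direction nor the size of f, so the values below are assumptions.

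| Assumed f | 7.1 dates (p = 0.401) | 8.1 dates (p = 0.135) |
|---|---|---|
| 20% | 8.0% fall | 2.7% fall |
| 30% | 12.0% fall | 4.1% fall |
| 50% | 20.1% fall | 6.8% fall |

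A rise of the same size gives the same figures with the opposite sign. If the comparison were run on the July 2020 to June 2021 window, p = 1 and the whole of f would pass through. As a yardstick only, section 5.1 powers the randomised comparison for a 20% reduction. On the 7.1 dates it takes an assumed fall of about 50% (0.20/0.401), sustained over all 476 days, to match that.

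**3. What a between-arm contrast would do.** Write θ for the effect of the intervention relative to EUC, and suppose that the pandemic shift is common to both arms.

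- Intervention arm, after/before: θ × (1 − p × f)
- EUC arm, after/before: 1 − p × f
- Ratio of the two: θ

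The shift cancels in the ratio, but section 7.2 plans the first two quantities and not the third.

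**4. Consistency of the definitions.** The control arm's reference is the time before the trial, and the intervention arm's is the time before CYPHP. Because 2017/18 lies between the baseline years and the trial start, and some implementation began in that year, these need not be the same period. Version B is labelled the quasi-experimental population and consists of pilot and intervention clusters, whereas section 8.1 defines that population as including the control clusters too.

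**The case against.** The strongest reply is that these analyses carry little inferential weight. The main analysis in section 10.9 is a concurrent randomised comparison, in which a shared pandemic shift acts on both arms, and it already adjusts for the cluster's baseline rate of the same endpoint. Section 7.2 attaches no hypothesis to the before/after work, and it places an equivalent comparison in the EUC arm beside it, where a common shift would be visible. All of this stands. A reader might infer that the plan would report the COVID fall in admissions as a CYPHP effect. The documents do not support that: they record no fall, nowhere say the single-arm change will be attributed to CYPHP, and rest the main inference on the randomised contrast.

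A reader might also take 40% as the settled pandemic share. It holds only on the section 7.1 dates; section 8.1 gives 13.5%. Nor does section 7.1 tie the July 2020 to June 2021 window specifically to the before/after comparisons. The time series is described only by its periods, so its model is unspecified rather than shown to be uncontrolled. The contents of the appendix diagrams of time periods and of the COVID pause are not available in the text reviewed and might bear on the periods used.

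What the reply does not remove is the missing contrast. Two separate before/after results, with differently worded reference periods, yield no estimate or confidence interval for the difference in change. The EUC change is also not a pure calendar effect, since EUC is itself enhanced care.

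**Conclusion.** The point holds for the supplementary analyses in section 7.2. As written, the intervention-arm before/after estimate combines any CYPHP effect with any calendar shift since March 2017, and nothing in the stated analysis separates them. The exposed share is 40.1% on the 7.1 dates or 13.5% on the 8.1 dates. An assumed pandemic fall of 20% to 50% would give a spurious reduction of 8% to 20%, or of 2.7% to 6.8%, respectively.

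These sizes rest on the pause date as a proxy for the pandemic's start, on evenly spread person-time, and on a fall whose direction and size are not in the documents. The main randomised comparison is untouched, so this is a worthwhile improvement and not a threat to the primary result.

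**What to change.** 1. Reconcile the end date in section 7.1 (June 2021) with that in section 8.1 (June 2020), and state which period section 7.2 uses. Define the before period identically for both arms.
2. Estimate the before/after effect in one model with arm, period, arm-by-period interaction and calendar time, with clustering by GP hub. The interaction, with its confidence interval, is the result to report. In the quasi-experimental version keep the control clusters, as section 8.1 defines that population.
3. In the interrupted time series, use the control arm as the comparison series.
4. Label single-arm before/after figures descriptive, or end them at 11 March 2020.

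**Cost.** Sections 6.1 and 6.2 already provide for primary care and hospital data from practices in both arms, so no new collection is needed. The work is more than wording, however. Section 10.9 describes one trial-period count per child, and counts and person-time would have to be split by calendar period. Truncation at 11 March 2020 would leave 1187 − 476 = 711 trial days and would drop the later window that section 7.1 regards as having the fullest embedding of services. The interaction also assumes that the pandemic acted equally on both arms, which should be stated.

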8. STUDY POPULATIONS

8.1 Health Service Use Population level populations

Inclusion criteria:

- Aged 0-15 (<16) years
 - Within the study period (April 2018 to June 2020)
- Registered with a randomised Southwark or Lambeth GP practice
 - Within the study period (April 2018 to June 2020)

This will be an open cohort, including children who register with a GP practice during the course of the trial. Trial arm assignment is described in section 18.

Exclusion criteria:

We excluded children who had <30 days observation time. Reasons for short observation time include

- Children turning 16 years shortly after the start of the trial period,
- Children registering with a GP practice shortly before the end of the trial period.

➤ Randomised population

Intervention and control only, *excluding* pilot clusters or practices where the randomisation allocation could not be determined.

➤ Quasi-experimental population

Intervention, control *and* pilot clusters

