8.2 Health Service Use Tracer condition populations

Subset of populations in section 8.1, excluding those without a tracer condition (asthma, constipation, or eczema).

Definition of tracer condition: Uses the same methodology applied by the CYPHP call/recall system, i.e. diagnosis, disease management, or therapy codes in the primary care record, and age restrictions. The clinical (Read/SNOMED) codes and therapies are listed in Appendix. For all conditions, an individual's complete records are interrogated.

If a subject meets the call/recall criteria for a tracer condition, they are defined as having a tracer condition from the first recorded event used in the definition (e.g. if they are defined as having asthma due to having an asthma diagnosis or three prescriptions of asthma medication in one year, we define their asthma 'start date' as the date of the first of those prescriptions or diagnosis).

We treat all conditions as ongoing, i.e. the observation period is continuous from the 'start date' of their condition (described above) until their observation 'end date' which occurs when they leave a GP practice, turn 16 years of age, or reach the end of the study period.

➤ Randomised HSU Tracer condition population

Intervention and control only, *excluding* pilot clusters

Subpopulations:

- Asthma
- Eczema
- Constipation

➤ Quasi-experimental HSU Tracer condition population

Intervention, control *and* pilot clusters

Subpopulations:

- Asthma
- Eczema
- Constipation

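### SAP 8.1 closes eligibility for the primary-outcome cohort in June 2020, a year before the trial end in 7.1 and one day before the planned secondary window opens

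*SAP*

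**What the plan says.** Section 8.1 gives two inclusion criteria for the population health service use cohort, age 0 to 15 and registration with a randomised practice. Each carries the same limit: "Within the study period (April 2018 to June 2020"). The section then says "This will be an open cohort, including children who register with a GP practice during the course of the trial". It also says "We excluded children who had <30 days observation time", and one reason it gives for short observation is "Children registering with a GP practice shortly before the end of the trial period".

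Section 7.1 starts the trial on 1 April 2018 and then states "Trial period ends: 30 June 2021". It adds a secondary analysis: "Using the trial time period 1 July 2020 - 30 June 2021 (the period with most complete embedding of services").

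Section 10.9, which governs the main comparison of arms, sends the reader to section 8 for populations and to section 7 for the time period. Section 8.2, the tracer-condition subset of 8.1, stops a child's observation on leaving the practice or when they "turn 16 years of age, or reach the end of the study period".

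**The concern.** Section 8.1 is the inclusion rule for the primary population outcome, and its end date differs by a year from the trial period over which that outcome is to be analysed. A child born after June 2020 is at no time aged 0 to 15 inside the 8.1 window. A child first registered after June 2020 is at no time registered inside it. Both fail inclusion, although 7.1 counts the following year as trial time and singles it out as the year when services were best embedded.

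Two analysts working from this text could build different cohorts. One would code the inclusion criteria as printed; the other would follow 10.9 back to section 7. What is at stake is whom the estimate describes, whether it can be reproduced, and whether the secondary analysis has a defined population. If the choice is left until outcome data by arm have been seen, it is no longer pre-specified.

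**Working it through.** **Dates (inclusive, SAP 7.1 and 8.1)**

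- 8.1 window, 1 April 2018 to 30 June 2020: 822 days, 27 months.
- 7.1 trial period, 1 April 2018 to 30 June 2021: 1187 days, 39 months.
- Difference: 1187 − 822 = 365 days.
- Secondary window, 1 July 2020 to 30 June 2021: 365 days. It opens the day after the 8.1 window closes, so the overlap is 0 days.

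**Three readings**

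*A. Everything runs to June 2021, and the date in 8.1 is out of step.* Nothing is lost once 8.1 is corrected.

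*B. The study period ends both eligibility and observation in June 2020.* Section 8.2 ends observation at the end of the study period, and 8.1 is the only place in the text that puts dates to that term. The secondary window then has no person-time, and 365/1187 = 31% of the trial period in 7.1 is lost.

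*C. Entry closes in June 2020 but observation runs to June 2021.* Children already in the cohort still contribute, and new births and new registrants are lost.

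**Size under reading C, births only (illustration)**

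Input from SAP 5.1: 89,382 CYP aged 0 to 15 registered in 2015. Assumptions not in the SAP: births uniform over the year, registration at birth, and an under-1 share of 1/16 (range 5% to 8%).

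1. A child born with k days left in the secondary window gives k days, k = 1 to 365. Section 8.1 drops k < 30 in any case, leaving 336 of 365 birth days.
2. Children lost: 89,382 × share × 336/365. At 5% this is 4,114; at 1/16, 5,143; at 8%, 6,582.
3. Person-days lost per one birth per day: (1 + … + 365) − (1 + … + 29) = 66,795 − 435 = 66,360.
4. Fraction of under-1 person-time in the secondary window: 66,360/365² = 0.498.
5. Fraction of all person-time in the secondary window: 0.498 × share = 2.5% (5%), 3.1% (1/16), 4.0% (8%).
6. Over the full period of 1187/365 = 3.25 years: 0.498/3.25 = 15.3% of under-1 time, and 15.3% × share = 0.8%, 1.0%, 1.2% of all person-time.

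Older children who first register after June 2020 would add to this. The SAP gives nothing from which to count them.

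**The case against.** The strongest reply is that this is a date left uncorrected. Section 10.9 sends the analysis period to section 7, the secondary window is called trial time, and population reporting in Q4 2021 (section 20) fits data to June 2021. On that view any analyst would use June 2021 and nothing would be lost. Most of the text does point that way. But June 2020 is printed twice, inside the formal inclusion criteria, and no text shown reconciles it with 7.1. The time-periods diagram (23.3) and the table of outcomes and populations (23.1) are not available here and cannot settle it.

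Stronger conclusions are tempting but are not supported:

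- *That 8.1 contradicts itself.* Its references to the course and end of the trial fit a trial ending in June 2020. They clash only once the end date in 7.1 is brought in. The conflict is between sections.
- *That the loss is of new entrants only, at the sizes shown for reading C.* The SAP nowhere separates the end of entry from the end of observation, so those figures are conditional on a split that it does not state.
- *That the trial pause (18.1) or the first phase of about two years (1.1) explains the date.* The effects stated in 18.1 concern data collection from consented participants and the timing of their follow-up, not entry to the routine-data cohort. Section 1.1 describes the planned roll-out, not an analysis window.
- *That the comparison is biased between arms.* The rule is identical in both arms, and nothing in the SAP shows a differential effect.

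**Conclusion.** The point holds as a conflict of dates between 7.1 and 8.1 in the inclusion rule for the primary population outcome. Section 8.2 inherits it through its undated reference to the study period. The 365-day gap and the zero overlap with the secondary window follow directly from the SAP and need no assumption. The consequence does depend on the reading. It ranges from nothing, if 8.1 is simply corrected, through about 1% of all person-time over 39 months and 2.5% to 4.0% in the secondary window (births only, under the assumptions listed), to 31% of the trial period and an empty secondary analysis. The populations in 8.3 to 8.5 are tied to the Health Check or consent date and do not use this end date. This should be fixed, because the present wording does not define one reproducible cohort.

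**What to change.** Before unblinding, amend 8.1 so that eligibility and end of observation both use the trial period in 7.1, 1 April 2018 to 30 June 2021. Use the same term and dates in 8.2. State that 1 July 2020 to 30 June 2021 is a secondary window nested within that period. If June 2020 is intended in 8.1, say so, and give separate eligibility and observation dates for the primary and the secondary windows.

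The cost is a change of wording in the SAP. Section 7.1 already calls for data to June 2021, and the Q4 2021 reporting date already fits, so no new data are needed.
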